There were case reports originating from the 1970s about concerns over high dose oxytocin and its association with maternal hyponatremia or water intoxication ^{25,26}. The hypothesis behind its association is due to the similarity between oxytocin and anti-diuretic hormone. These were largely single case reports in the setting of accidental large overdose of oxytocin in addition to administration of large volumes of electrolyte-free solutions. Since then, the practice of administering oxytocin is only given alongside isotonic lactated ringer or normal saline in a slow intravenous infusion fashion ^{27,28}. In addition, there were also some case series showing that a large amount of oxytocin given intravenously as a bolus can cause maternal hypotension, tachycardia and EKG changes ^{29,30}. In a similar fashion, these changes were observed due to a very large amount of IV boluses given over a short amount of time, which is a very different practice than how oxytocin is now administered on labor and delivery via a slow intravenous infusion.

- 1. IOM (Institute of Medicine) and NRC (National Research Council). 2009. Weight Gain During Pregnancy: Reexamining the Guidelines. Washington, DC: The National Academies Press.
- 2. Obesity in pregnancy. Practice Bulletin No. 156. American college of obstetricians and gynecologists. Obstet Gynecol 2015; 126:e112-26.
- 3. Carlson et al. Parturition dysfunction in obesity: time to target the pathobiology. Reproductive and endocrinology (2015) 13:135.

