4. Intervention group: Obese cohort: BMI ≥30, at <20 weeks gestation or BMI ≥35 at a term gestation of pregnancy, high dose oxytocin protocol

Lean cohorts will be randomized into the low dose or high dose oxytocin arm. The obese cohorts will also be randomized into the low dose or high dose oxytocin arm.

Protocol for each comparison group

Management of oxytocin induction in this study follows normal standard of care on labor and delivery nationally. The only part which will be done specifically for research is the higher concentration of oxytocin given in this study in the high dose oxytocin arm.

Per routine care, oxytocin dosage is titrated up or down to achieve labor while maintaining patient safety. Patient safety is continuously monitored with the tocometer (to monitor for maternal uterine contractions) and fetal heart tracing (to monitor for fetal well being). Stopping rules are listed under each arm separately.

1) Lean, low dose oxytocin arm

Oxytocin will be administered as described above via a slow intravenous infusion pump. Under the supervision of the study investigator, the patient's nurse will increase the oxytocin infusion as described above, start at 2cc/hr, increase 2cc/hr every 30 minutes up to 20cc/hr. The oxytocin will be increased until one of the parameters below were met:

>200 Montevideo unit on an intrauterine pressure catheter

3-5 uterine contractions in a 10-minute period on the external uterine tocometer cervical change and progression of labor

Tachysystole is defined as more than 5 contractions in 10 minutes over an average of a 30 minutes period. In the setting of tachysystole with reassuring fetal status, the oxytocin would be decreased by increments of 2cc until tachysystole no longer occurs. In the setting of nonreassuring fetal status (determined by the provider based on the fetal heart tracing), the oxytocin infusion would be turned off and restarted at ½ of the previous dose after 30 minutes, as long as fetal heart tracing recovers.

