Similarly, regardless of tachysystole, if nonreassuring fetal status occur (at the discretion by the provider), the oxytocin infusion will be turned off and restarted at ½ of the previous dose after 30 minutes, as long as fetal heart tracing recovers. If fetal heart tracing does not recover, the general protocol on labor and delivery would generally warrant an expedited delivery via cesarean delivery. This decision will be made at the discretion of the provider. Therefore, cesarean delivery and operative vaginal delivery is reserved for the usual indications determined by the provider.

Monitoring of maternal urine output is routinely done on labor and delivery every 4 hours. If oliguria occurs (<0.5cc/kg/hour), a basic metabolic panel will be obtained to assess for hyponatremia. If the sodium level is below 130 meq/L, the oxytocin infusion will be turned off until resumption of urine output or rise in sodium level to above 130meq/L.

Patient will remain in nothing per oral status per routine guidelines on labor and delivery. Patient can receive other common obstetrical intervention per usual, including epidural placement for pain control, artificial rupture of membrane for labor progression, internal intrauterine pressure

catheter or fetal scalp electrode placement for closer monitoring. Similarly, management of 2nd stage of labor after achieving full cervical dilation will be managed per routine care.

Subsequently after delivery, a new bag of usual concentration of oxytocin will be used in all 4 groups for postpartum oxytocin as per routine.

2) Lean, high dose oxytocin arm

Oxytocin will be administered as described above via a slow intravenous infusion pump. Under the supervision of the study investigator, the patient's nurse will increase the oxytocin infusion as described above, start at 2cc/hr, increase 2cc/hr every 30 minutes up to 20cc/hr. The oxytocin will be increased until one of the parameters below were met:

>200 Montevideo unit on an intrauterine pressure catheter

3-5 uterine contractions in a 10-minute period on the external uterine tocometer cervical change and progression of labor

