Tachysystole is defined as more than 5 contractions in 10 minutes over an average of a 30 minutes period. In the setting of tachysystole with reassuring fetal status, the oxytocin would be decreased by increments of 2cc until tachysystole no longer occurs. In the setting of nonreassuring fetal status (determined by the provider based on the fetal heart tracing), the oxytocin infusion would be turned off and restarted at ½ of the previous dose after 30 minutes, as long as fetal heart tracing recovers.

Similarly, regardless of tachysystole, if nonreassuring fetal status occur (at the discretion by the provider), the oxytocin infusion will be turned off and restarted at ½ of the previous dose after 30 minutes, as long as fetal heart tracing recovers. If fetal heart tracing does not recover, the general protocol on labor and delivery would generally warrant an expedited delivery via cesarean delivery. This decision will be made at the discretion of the provider. Therefore, cesarean delivery and operative vaginal delivery is reserved for the usual indications determined by the provider.

Monitoring of maternal urine output is routinely done on labor and delivery every 4 hours. If oliguria occurs (<0.5cc/kg/hour), a basic metabolic panel will be obtained to assess for hyponatremia. If the sodium level is below 130 meq/L, the oxytocin infusion will be turned off until resumption of urine output or rise in sodium level to above 130meq/L.

Patient will remain in nothing per oral status per routine guidelines on labor and delivery. Patient can receive other common obstetrical intervention per usual, including epidural placement for pain control, artificial rupture of membrane for labor progression, internal intrauterine pressure catheter or fetal scalp electrode placement for closer monitoring. Similarly, management of 2nd stage of labor after achieving full cervical dilation will be managed per routine care.

Subsequently after delivery, a new bag of usual concentration of oxytocin will be used in all 4 groups for postpartum oxytocin as per routine.

3) Obese, low dose oxytocin arm

Oxytocin will be administered as described above via a slow intravenous infusion pump. Under the supervision of the study investigator, the patient's nurse will increase the oxytocin infusion as described above, start at 2cc/hr, increase 2cc/hr every 30 minutes up to 20cc/hr. The oxytocin will be increased until one of the parameters below were met:

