- >200 Montevideo unit on an intrauterine pressure catheter
- 3-5 uterine contractions in a 10-minute period on the external uterine tocometer cervical change and progression of labor

Tachysystole is defined as more than 5 contractions in 10 minutes over an average of a 30 minutes period. In the setting of tachysystole with reassuring fetal status, the oxytocin would be decreased by increments of 2cc until tachysystole no longer occurs. In the setting of nonreassuring fetal status (determined by the provider based on the fetal heart tracing), the oxytocin infusion would be turned off and restarted at ½ of the previous dose after 30 minutes, as long as fetal heart tracing recovers.

Similarly, regardless of tachysystole, if nonreassuring fetal status occur (at the discretion by the provider), the oxytocin infusion will be turned off and restarted at ½ of the previous dose after 30 minutes, as long as fetal heart tracing recovers. If fetal heart tracing does not recover, the general protocol on labor and delivery would generally warrant an expedited delivery via cesarean delivery. This decision will be made at the discretion of the provider. Therefore, cesarean delivery and operative vaginal delivery is reserved for the usual indications determined by the provider.

Monitoring of maternal urine output is routinely done on labor and delivery every 4 hours. If oliguria occurs (<0.5cc/kg/hour), a basic metabolic panel will be obtained to assess for hyponatremia. If the sodium level is below 130 meq/L, the oxytocin infusion will be turned off until resumption of urine output or rise in sodium level to above 130meq/L.

Patient will remain in nothing per oral status per routine guidelines on labor and delivery. Patient can receive other common obstetrical intervention per usual, including epidural placement for pain control, artificial rupture of membrane for labor progression, internal intrauterine pressure catheter or fetal scalp electrode placement for closer monitoring. Similarly, management of 2nd stage of labor after achieving full cervical dilation will be managed per routine care.

Subsequently after delivery, a new bag of usual concentration of oxytocin will be used in all 4 groups for postpartum oxytocin as per routine.

4) Obese, high dose oxytocin arm

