Oxytocin will be administered as described above via a slow intravenous infusion pump. Under the supervision of the study investigator, the patient's nurse will increase the oxytocin infusion as described above, start at 2cc/hr, increase 2cc/hr every 30 minutes up to 20cc/hr. The oxytocin will be increased until one of the parameters below were met:

- >200 Montevideo unit on an intrauterine pressure catheter
- 3-5 uterine contractions in a 10-minute period on the external uterine tocometer cervical change and progression of labor

Tachysystole is defined as more than 5 contractions in 10 minutes over an average of a 30 minutes period. In the setting of tachysystole with reassuring fetal status, the oxytocin would be decreased by increments of 2cc until tachysystole no longer occurs. In the setting of nonreassuring fetal status (determined by the provider based on the fetal heart tracing), the oxytocin infusion would be turned off and restarted at ½ of the previous dose after 30 minutes, as long as fetal heart tracing recovers.

Similarly, regardless of tachysystole, if nonreassuring fetal status occur (at the discretion by the provider), the oxytocin infusion will be turned off and restarted at ½ of the previous dose after 30 minutes, as long as fetal heart tracing recovers. If fetal heart tracing does not recover, the general protocol on labor and delivery would generally warrant an expedited delivery via cesarean delivery. This decision will be made at the discretion of the provider. Therefore, cesarean delivery and operative vaginal delivery is reserved for the usual indications determined by the provider.

Monitoring of maternal urine output is routinely done on labor and delivery every 4 hours. If oliguria occurs (<0.5cc/kg/hour), a basic metabolic panel will be obtained to assess for hyponatremia. If the sodium level is below 130 meq/L, the oxytocin infusion will be turned off until resumption of urine output or rise in sodium level to above 130meq/L.

Patient will remain in nothing per oral status per routine guidelines on labor and delivery. Patient can receive other common obstetrical intervention per usual, including epidural placement for pain control, artificial rupture of membrane for labor progression, internal intrauterine pressure catheter or fetal scalp electrode placement for closer monitoring. Similarly, management of 2nd stage of labor after achieving full cervical dilation will be managed per routine care.

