A data collection sheet will be used to record data. This data will then be stored in a coded fashion with key code assigned, in a computer excel spreadsheet on the principal investigator's computer, located in room 8327G in the Department of Obstetrics and Gynecology. Only the PI will have access to the key code. Because every account on the computer is password protected, the only person who has access to this computer is the PI herself. Only personnel on the VOTF will be granted access to this data/spreadsheet. The data collection sheet and the patient consent forms will be kept in the same room in a locked file cabinet. These data collection sheets, the patient consent documents as well as the key code will be stored for a period of 6 years after conclusion of study and destroyed thereafter.

13) Access to Private Information

a. Access to medical records (HIPAA): Patients agreeing to participate in this study will be made aware that record review of their, and their child's, protected health information will occur as a part of the study. The consent form includes HIPAA consent. Only investigators on the VOTF can access their PHI, as described above. A list of data to be collected is detailed above.

14) Subject compensation

There will be no monetary compensation provided to the subjects for participating in this study.

15) Medical care and compensation for injury

There are no expected maternal or fetal injuries attributed to the high dose oxytocin regimen compared to the low dose oxytocin regimen as discussed above. In the unforeseeable event that a complication occurs, the patient will be billed for their medical care as they would with any other induction of labor.

16) Monitoring for subject safety

The study protocol has built in monitoring measures for specific clinical scenarios in the setting of adverse reactions. These include specific detailed protocols for tachysystole, nonreassuring fetal status as well as oliguria.

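### In all four arms, an oxytocin hold for sodium below 130 meq/L may end on return of urine output alone, with no repeat sodium required

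*Combined protocol and SAP*

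**What the plan says.** Section 8 introduces the arm descriptions with "Stopping rules are listed under each arm separately". Each of the four descriptions then carries the same paragraph on urine output, which is checked every 4 hours:

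- Test: "If oliguria occurs (<0.5cc/kg/hour), a basic metabolic panel will be obtained to assess for hyponatremia".
- Hold: "If the sodium level is below 130 meq/L, the oxytocin infusion will be turned off".
- Release, in the same sentence: "the oxytocin infusion will be turned off until resumption of urine output or rise in sodium level to above 130meq/L".

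The paragraph asks for no second sodium, and no other section does.

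Section 16 counts this among the built-in safety measures: "These include specific detailed protocols for tachysystole, nonreassuring fetal status as well as oliguria".

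Section 10 lists hyponatremia among the SAEs and gives no sodium value. Sections 10 and 16 both say that an SAE ends the study protocol at once, and that the protocol describes how AEs are managed.

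**The concern.** Oliguria alone does not stop the drug; it only prompts the blood test. The sodium result turns an oliguric woman into a woman whose infusion is stopped. Yet the infusion may be restarted without anyone showing that this result has improved.

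Urine output is relevant evidence but not a substitute. On the link between oxytocin and hyponatremia, the Background says: "The hypothesis behind its association is due to the similarity between oxytocin and anti-diuretic hormone". On that account, returning urine output suggests that the antidiuretic effect has eased. It does not measure sodium. Once the hold is released on urine output, the protocol prompts another sodium only if oliguria is found again at a later 4-hourly check.

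What is at stake is the safety of the few women held, and whether staff have one clear instruction for a sodium below 130.

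**Working it through.** No figure in the plan needs to be reproduced; the check is one of logic.

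**Step 1. Inputs, all from Section 8 and identical in the four arms.** The hold needs two things together: oliguria and sodium below 130. Release needs either of two things: urine output returned, or sodium above 130.

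**Step 2. List the states at reassessment.** The sodium column is the true value, which under the current rule may not have been measured.

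| Urine output | Sodium (meq/L) | Current rule | Release only on repeat sodium above 130 |
|---|---|---|---|
| Returned | above 130 | restart allowed | restart allowed |
| Returned | exactly 130 | restart allowed | hold |
| Returned | below 130 | restart allowed | hold |
| Not returned | above 130 | restart allowed | restart allowed |
| Not returned | exactly 130 | hold | hold |
| Not returned | below 130 | hold | hold |

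**Step 3. Count.** The current rule allows a restart in 3 + 1 = 4 of 6 states; the sodium-only rule allows it in 2 of 6. Removed: 4 − 2 = 2, both with urine returned and sodium not above 130. Added: 0. If exactly 130 and below 130 are merged, the counts are 3 of 4 against 2 of 4, with 1 removed and 0 added. These are counts of logical states and say nothing about how often each occurs.

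**Step 4. Compare alternative fixes.**

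- Release at 130 or above would free a still-oliguric woman at exactly 130, whom the current rule holds. That adds a state, so the existing threshold is kept.
- Requiring both urine output and sodium above 130 would allow a restart in 1 of 6 states. It would go on holding women whose sodium is corrected but who are still oliguric, and the concern does not call for that.

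**Step 5. Set the hold beside the SAE rule.** There are two cases.

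- If sodium below 130 is the hyponatremia listed in Section 10, the study protocol ends and the release clause in Section 8 can never apply.
- If it is not, the hold applies and the gap in Step 2 is live.

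The documents do not say which. The value 130 is the only sodium cut-off given, and the test is drawn specifically to look for hyponatremia, which favours the first case. Sections 10 and 16 leave the management of AEs to the protocol, which favours the second. It is also unclear whether ending the study protocol refers to the woman's treatment or to the trial. Either way, it does not fit with resuming her study infusion.

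**The case against.** The best defence is that the release rule is coherent. The hold needs oliguria and low sodium together, so releasing when either one clears is, apart from the value of exactly 130, the logical negation of the trigger. A woman with normal urine output would never have been tested or held. This stands as a point of logic, and it makes sodium-only release a clinical judgement rather than the repair of a contradiction. It does not remove the concern: the woman held has a known low sodium, and after release the rule treats her like a woman whose sodium was never in question.

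Safeguards outside the rule also count. Physicians are in house around the clock and may recheck sodium. The drug is given in 0.9% saline at 2 to 20 cc/hour before provider reassessment. But providers are blinded to concentration, and at 20 cc/hour the two regimens deliver 20 and 60 miliunit/minute. Staff cannot adjust their caution to the dose, so the written rule matters more than usual.

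A reader might infer several stronger things that the documents do not support:

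- **That the protocol directs a restart at low sodium.** It permits one; nothing stops a provider from retesting.
- **That this is the only safety rule that can end with its trigger uncorrected.** Tachysystole with reassuring fetal status is handled so that "the oxytocin would be decreased by increments of 2cc until tachysystole no longer occurs". When fetal status is nonreassuring, however, the restart is at half "of the previous dose after 30 minutes, as long as fetal heart tracing recovers", and clearance of tachysystole is not a stated condition.
- **That Section 8 flatly contradicts the SAE rule.** The conflict exists only if sodium below 130 is the listed event. In that case the release gap is not live, so the two problems should not be added together. Nor is the ambiguity peculiar to sodium: fetal bradycardia, maternal tachycardia and hypotension are also listed as SAEs without cut-offs.

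**Conclusion.** The concern holds in a limited form. As written, the rule in all four arms allows oxytocin to restart without a repeat sodium, and possibly with sodium still below 130 meq/L. This rests on the ordinary meaning of the release condition and on the absence of any retest requirement elsewhere.

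The frequency cannot be estimated from the documents. Section 10 calls the listed risks rare apart from tachysystole and nausea and vomiting, so few women are likely to be affected. There is no consequence for the sample size or the primary comparison. This is an inexpensive safety improvement, not a flaw in the trial's inference.

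The SAE question is secondary and conditional, but it needs an answer: staff cannot tell from the text whether a sodium below 130 means hold and resume or end the study protocol.

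**What to change.** 1. In each of the four arm descriptions in Section 8, replace the release condition with: *until a repeat sodium is above 130 meq/L*.
2. State once, consistently across Sections 8, 10 and 16, whether a sodium below 130 is managed by this hold or is the hyponatremia SAE that ends the study protocol. If the SAE rule governs, the hold-and-resume text should go and change 1 falls away. No lower cut-off is proposed here: the documents give no basis for one, and choosing one is a clinical trade-off for the investigator.

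The cost is one sentence changed in four places and a clarifying line. Each woman held needs at least one repeat blood test. Some holds will last longer, which could lengthen time to delivery in those few women.

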These are well known side effects of oxytocin on the obstetrical floor and the absolute rates remain low. Again, as discussed above, these risks were evaluated and compared directly by multiple meta-analysis and a Cochrane review. There was also no difference in serious maternal or neonatal morbidity or death between the high and low dose regimen. There was no difference in adverse outcomes, including maternal uterine rupture, postpartum hemorrhage, endometritis, estimated blood loss, abnormal fetal heart tracing, fetal Apgar, newborn resuscitation and neonatal intensive care unit admission ³⁻⁵. Therefore, the investigator believes that the risk to the patient will be similar to baseline.

Tachysystole will be monitored continuously as a clinical parameter to direct patient care and protocol management as well as a secondary outcome variable.

Endocrine and metabolic: Water intoxication (SAE), hyponatremia (SAE)

Again, as described above, there were also old case reports originating from the 1970s about concerns over high dose oxytocin and its association with maternal hyponatremia or water intoxication ^{6,7}. The hypothesis behind its association is due to the similarity between oxytocin and anti-diuretic hormone. These were largely single case reports in the setting of accidental large overdose of oxytocin in addition to large volume administration of electrolyte-free solutions. Since then, the practice of administering oxytocin is only given alongside isotonic lactated ringer or normal saline in a slow intravenous infusion fashion ^{8,9}. This study does not deviate from the standard of care. Therefore, the investigator predicts a low risk to patients, risks that would be comparable with current standard of care.

The following SAE and AE have been associated with oxytocin but frequency is not well defined and not well reported in the literature.

Hematologic: pelvic hematoma (SAE), fatal afibrinogenemia (SAE)

Misc: Anaphylactic reaction (SAE), nausea and vomiting (AE)

Risks to fetus include:

Due to induced uterine motility: bradycardia (SAE), premature ventricular contractions and other arrhythmias (SAE), permanent CNS or brain damage (SAE), fetal death (SAE), neonatal seizures (SAE)

Due to use of oxytocin in mother: low apgar scores (AE), neonatal jaundice (AE), neonatal retinal hemorrhage (SAE)

Frequency of risks:

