The frequency of risks occurring for each risk is not well defined and not well reported in the literature. All above risks are considered to be rare, with the exception of:

Tachysystole: This will be monitored continuously as a clinical parameter to direct patient care and protocol management, as written in the protocol. Also it is important to recognize that tachysystole occurs with the low dose protocol as well, which is the current standard of care.

Nausea and vomiting: This is a common side effect of labor itself with or without oxytocin.

It is important to recognize that these risks exist equally in the low dose protocol, which is the current standard of care on Labor and Delivery. When a patient presents for an induction of labor with oxytocin, they are subjected to all of the above risks, regardless of whether they are enrolled as a study participant. The only way to avoid these risks completely, is for a patient to not receive oxytocin (which is required if patient agreed to undergo an induction of labor). These risks above have been well monitored throughout clinical practice since the 1970s, and large Cochrane review as detailed above had provided good safety profile for this drug in both the low and high dose regimen.

All serious adverse events (SAE) will be monitored and documented closely during the study, and will result in discontinuation of the study protocol immediately. The management of AE is detailed in the protocol. If more than 20% of patients enrolled in the study have an AE/SAE, enrollment in the study will be stopped pending an evaluation of the frequency of AE/SAE.

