For every 10 enrollments, data will be monitored by the principal investigator and reviewed by an independent reviewer within the department of ob/gyn. This personnel will have a background in ob/gyn and will be assigned by the principal investigator. Data will be reviewed in a blinded fashion to prevent introducing bias into the study. In addition, all serious adverse events (SAE) will be monitored and documented closely during the study with each enrollment, and will result in discontinuation of the study protocol immediately. The management of AE is detailed in the protocol. If more than 20% of patient enrolled in the study have an AE/SAE, enrollment in the study will be stopped pending an evaluation of the frequency of AE/SAE. This will be reported to the IRB. The principal investigator and the research staffs will monitor protocol adherence closely with each enrolled participant. Any protocol deviation will be reported to the IRB as required.

17) Withdrawal of subjects

A patient may withdraw from this research at any time. The infusion of the study drug can be stopped at any time. A patient may withdraw for any reason, including a desire to stop induction of labor and undergo an elective cesarean delivery. Subjects will not be at increased risk when they are abruptly withdrawn from the study because of the short half-life of oxytocin (4.5 minutes). Data collection on patients who have completed more than 30 minutes of study drug will be kept and included in the data analysis (intention to treat analysis). Any withdrawal secondary to side effects or adverse effects will be recorded and monitored. Only verbal withdrawal is required.

18) Sharing of results with subjects

The results of the study will not be shared with the subjects, families or the institution. Patients will not be contacted in the future in relation to the results of the research. The intention is to publish the results of this research and patients will have access to the information gained through this forum.

There will be no additional charges billed to the insurance for any procedures associated with this study.

19) Future use and long-term storage of data or specimens

Data will not be kept for future research.

20) Clinical Trials.gov Information

	ClinicalTrials.gov "NCT" number for this trial (provide):
\boxtimes	Registration pending
	Clinical trial does not require registration (explain):

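### Sodium below 130 meq/L, and by inference a nonreassuring fetal bradycardia that recovers, fall under two incompatible rules: section 8 resumes study oxytocin, sections 10 and 16 end the study protocol

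*Combined protocol and SAP*

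**What the plan says.** **Arm rules (section 8, Protocol for each comparison group).** The introduction states: "Stopping rules are listed under each arm separately". The same text then appears under each of the four arms.

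- Nonreassuring fetal status, as judged by the provider, with or without tachysystole: the infusion goes off and restarts at half the previous dose "after 30 minutes, as long as fetal heart tracing recovers".
- Oliguria triggers a metabolic panel to look for hyponatremia. If sodium is below 130 meq/L, "the oxytocin infusion will be turned off until resumption of urine output or rise in sodium level to above 130meq/L".

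**SAE list (section 10, Risks to subjects).** The maternal list has "Endocrine and metabolic: Water intoxication (SAE), hyponatremia (SAE"). The fetal list has "Due to induced uterine motility: bradycardia (SAE"). Neither entry carries a level, a duration or a recovery condition. Tachysystole is labeled an AE.

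**SAE rule (sections 10 and 16).** Section 10 says all SAEs are monitored and documented "and will result in discontinuation of the study protocol immediately". Section 16 repeats this: SAEs are followed "with each enrollment, and will result in discontinuation of the study protocol immediately". In both places the next sentence refers the management of AEs, and only AEs, to the protocol. Both sections also stop enrollment for an evaluation if more than 20% of enrolled patients have an AE or SAE.

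**Frequency.** Section 10 says the frequencies are poorly defined in the literature and adds "All above risks are considered to be rare", except for tachysystole and nausea or vomiting.

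**The concern.** Two staff members can each follow the protocol and handle the same woman in opposite ways. One returns her to her assigned concentration under section 8. The other takes her off it under section 10 or 16. Whichever is done departs from the other rule, and section 16 requires protocol deviations to be reported to the IRB.

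What is at stake is mainly safety conduct. The provider does not know whether the bag holds the single or the triple concentration, so the instruction has to be unambiguous and the same in every arm. It also bears on the comparison, because whether a woman stays on her assigned concentration would depend on which section her team happened to apply.

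**Working it through.** **1. The rules side by side**

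| Event | Section 8 (all arms) | Section 10 label | Sections 10 and 16 | Compatible? |
|---|---|---|---|---|
| Sodium below 130 meq/L | Off, then resumed when urine output returns or sodium exceeds 130 | SAE | Study protocol ends immediately | No, explicitly |
| Fetal bradycardia judged nonreassuring, then recovered | Off, restarted at half dose after 30 minutes | SAE | Study protocol ends immediately | No, by inference |
| Nonreassuring tracing without bradycardia, recovered | Off, restarted at half dose after 30 minutes | Not itself labeled | SAE rule not triggered by this alone | Yes |
| Tachysystole, reassuring fetus | Reduced in 2 cc steps | AE | AE management referred to the protocol | Yes |

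The first row needs no clinical inference, because the arm rule names hyponatremia and gives a level. The second does. The arm rules do not mention bradycardia; the link is the exclusion criteria in section 6, where prolonged bradycardia appears under non-reassuring fetal assessment.

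**2. The plan's own sample size**

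Inputs from section 6: 895 and 660 minutes (difference 235), SD 330, alpha 0.05, power 80%. Two-sided testing is assumed, since the plan does not say.

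n per group = 2 × (1.960 + 0.842)² × 330² / 235² = 30.95, rounded up to 31. This matches the plan. A one-sided test would give 25. At the planned 35 per group, a two-sample t-test has power 83.6%.

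**3. How likely the conflict is to arise**

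No rate is given, so p is assumed. P(at least one among 140) = 1 − (1 − p)^140.

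| Assumed p | Expected women (140p) | At least one |
|---|---|---|
| 0.5% | 0.7 | 50.4% |
| 1% | 1.4 | 75.5% |
| 2% | 2.8 | 94.1% |
| 5% | 7.0 | 99.9% |

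**4. Illustrative effect on power**

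Suppose a share d of the high-dose obese arm is discontinued and loses all or half of the 235-minute effect. The mean difference becomes 235 × (1 − d) or 235 × (1 − d/2). Power is for 35 per arm, SD 330, two-sided t-test.

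| d | Whole effect lost | Half lost |
|---|---|---|
| 1% | 232.7 min, 82.8% | 233.8 min, 83.2% |
| 2% | 230.3 min, 82.1% | 232.7 min, 82.8% |
| 5% | 223.3 min, 79.7% | 229.1 min, 81.7% |

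**5. Why this table does not bound the effect**

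If a discontinued woman's expected time is T instead of 660 minutes, the arm mean moves by d × (T − 660). At T = 895 and d = 1% that is 0.01 × 235 = 2.35 minutes, the first row above. Two facts leave T open. The documents do not say what a discontinued woman receives next, so T could exceed 895. And under section 2 the primary time ends at the decision for cesarean, so a discontinued woman who goes to cesarean could have T below 660, which would enlarge the apparent benefit.

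**The case against.** The strongest reply is that the intent is clear enough. Section 8 says the stopping rules sit under each arm, and section 16 presents the detailed procedures for tachysystole, nonreassuring fetal status and oliguria as the built-in response to adverse reactions. A specific rule would ordinarily prevail over a general sentence in a risk section. This stands as evidence of what was meant. It does not settle the matter: neither place mentions the SAE rule, and the sentence after that rule refers only AE management to the protocol, whereas these two events are labeled SAEs.

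A second reply is that the bradycardia half is inferential and that low sodium is found only through oliguria and then a blood test. The first part is right and limits the point to a bradycardia that the provider judges nonreassuring and that then recovers. The second affects how often the conflict arises, not whether the instructions agree.

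A third is rarity. Section 10 calls these risks rare, and the larger probabilities above need assumed rates of 2% to 5%. That limits the impact but does not remove the contradiction.

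Three stronger readings are tempting and are not supported:

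- That discontinuations must dilute the dose comparison, or that the power losses above are worst cases. Step 5 shows why neither follows.
- That every recovered nonreassuring tracing meets the conflict. Section 10 does not label such a tracing an AE or SAE, and section 2 treats abnormal tracing as a secondary outcome.
- That one such event closes the whole trial. The SAE sentence does not say whether it means the woman's participation or the study. Either meaning is incompatible with resuming her study oxytocin, so the point does not depend on it.

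**Conclusion.** The point holds. For sodium below 130 meq/L the two rules cannot both be followed, and this is explicit in the text. For a fetal bradycardia judged nonreassuring that then recovers, the same conflict follows by inference from the section 6 exclusion list. The arm rules were probably intended, but nothing says they take precedence.

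The statistical effect is small: under the illustrative assumptions, 0.8 percentage points of power at 1% discontinued (83.6 − 82.8) and 3.9 points at 5% (83.6 − 79.7). Its direction is unknown. These figures rest on assumed event rates, the planning difference and SD, and an assumed loss of effect. Intention to treat, stated in sections 6 and 17, already covers most of the analysis question. The case for change is therefore consistent safety conduct across four blinded arms. The change should be made, though the trial's main result does not hinge on it.

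**What to change.** **Sections 10 and 16.** After the SAE sentence, add:

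> Exception: a fetal bradycardia that recovers, and a hyponatremia whose sodium has risen above 130 meq/L, are recorded and reported as SAEs, count toward the 20% AE/SAE review, and have study drug managed by the section 8 rules. Study drug ends permanently if the tracing does not recover, for any other SAE, or if the provider decides.

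**Section 8, all four arms.** Once sodium below 130 meq/L has been found, require sodium above 130 before restart. The present wording accepts resumed urine output alone, so study drug, possibly at triple concentration, could restart with sodium still low.

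**Leave the 20% count otherwise unchanged.** Nonreassuring tracings without bradycardia should not be added to it; that would alter an enrollment-stopping trigger for events the plan does not class as AEs or SAEs.

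**Cost.** A short paragraph in two places and one altered sentence in each arm. A repeat sodium may be needed before restart, which can lengthen the pause. The data list in section 8 includes oliguria but not sodium, so the value would go in the SAE documentation that sections 10 and 16 already require. The main downside is that a woman whose event has resolved may return to study drug. Section 8 already allows this, but it is less protective than an immediate permanent stop, so the investigator and IRB should adopt it knowingly.
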